5. TRIAL DESIGN

5.1 Trial Plan

A prospective, single-center, randomized, blinded close-label study providing for the enrolment of a minimum of 16 to a maximum of 32 patients (see sample size in the section "Statistics") affected by NAION.

Considering that according to the inclusion/exclusion criteria it is very difficult to recruit patients suffering from NAION with the specific characteristics that enable them to be enrolled in this study, it is likely that with the presence of the binocular NAION, both eyes of the patients will be considered as recruited. Therefore, in the event of all patients having monocular NAION, enrolment must include 32 patients and this number is lower if we need to enrol patients with NAION in both eyes.

Patients selected according to the inclusion/exclusion criteria after signing informed consent will be randomized into two groups:

- a) In one group of patients with NAION no type of treatment will be performed (16 eyes, Control Group)
- b) in another group of patients with NAION, Citicoline will be administered in oral solution (500 mg/day) for 6 months followed by three months of suspension (16 eyes, Treated Group)

The division into two groups will enable the identification of a specific neuroprotective action of Citicoline. Randomization will be done by dividing patients with similar characteristics including age, refraction and visual impairment (perimeter defect and visual acuity) into two groups. Patients will be assigned to each group by an investigator not involved in the functional and structural tests.

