6. ASSIGNMENT AND MASKING

Patients will be selected from a large cohort of known NAION patients who have been attending our facility for at least 12 months (approximately 125 patients). Only patients who meet the inclusion criteria will be selected. Patients will perform a baseline screening visit during which the conditions corresponding to the inclusion criteria will be evaluated and the study proposed. Only after signing the informed consent, will a single investigator ("recruiting doctor"), not involved in the clinical and instrumental assessments, decide whether to assign the selected patient to the Citicoline-treated or non-Citicoline-treated group.

The assignment to either group will take place in sequential order of presentation of the patient (with a 1:1 probability of being assigned to one or the other group) in order to constitute two homogeneous groups in terms of number.

The aforementioned assignment will be known only to the patient and the "recruiting doctor" who will not be involved in the clinical and instrumental assessments envisaged by the research and will therefore be the only investigating doctor to know the group to which the selected patient belongs; this feature of the study will be used to ensure "objectivity" of the clinical and instrumental assessments and to prevent them from being influenced in any way by the knowledge that the patient examined has or has not been treated with Citicoline. In this regard, it should be noted that the patient, by signing the informed consent, promises not to provide any type of information regarding the group to which he/she belongs and/or any treatment administered to other staff of the Institute involved in the clinical and instrumental assessments apart from the "recruiting doctor".

As a result, throughout the duration of the study (both at baseline and at the 6 and 9 month visits),

all study assessments (AV, CV, VEP, PERG, OCT) will be conducted by investigators who do not know if the patient being examined belongs to the Citicoline-treated or non-Citicoline-treated group.

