9. STATISTICAL ANALYSIS

9.1 Sample size

The sample size is estimated based on the primary objective: 'assessment of stabilisation and/or improvement of visual acuity' (see section 2.1.).

This calculation is based on known preliminary data (Parisi et al, 2008), in which visual acuity was assessed through Early Treatment Diabetic Retinopathy Study (ETDRS) cards and the acquired value has been expressed in LogMAR (logarithm of the minimum angle of resolution).

Based on these known preliminary data (Parisi et al, 2008), and considering a power value = 90% ($\alpha = 5\%$) it is deemed reasonable to include in the study $N = 5$ observations (eyes tested) per group.

The sample size has been calculated based on the difference in visual acuity measured in patients with NAION after 60 days of treatment with Citicoline in oral suspension compared to the baseline of 0.35 LogMAR (baseline visual acuity: mean 0.621 LogMAR, a standard deviation: 0.122 LogMAR; visual acuity at 60 days: mean 0.271 LogMAR, a standard deviation: 0.107 LogMAR).

However, based on the secondary objective-point 2 (see section 2.2) 'to determine in patients with NAION the potential for neuroenhancement related to the administration of Citicoline oral solution. This will be achieved through functional condition assessments (PERG/VEP) measured after treatment with Citicoline compared to the condition at the time of recruitment", it is considered appropriate to assess the sample size taking into account the known preliminary data (Parisi et al, 2008) in which they were analysed:

- a) changes in the functionality of retinal ganglion cells by measuring the Amplitude P50-N95 (measured in microvolts) obtained by recording the ERG from Pattern (PERG).
- b) changes in optic nerve function by measuring Implicit Time P100 (measured in milliseconds, ms) obtained by recording Visual Evoked Potential (VEP).

Based on known preliminary data (Parisi et al, 2008), considering the P50-N95 amplitude of the PERG and a power value = 90% ($\alpha = 5\%$) it is reasonable to include in study $N = 12$ observations (eyes tested) per group. The sample number has been calculated based on the difference in the P50-N95 amplitude of the PERG measured after 60 days of treatment with Citicoline for oral suspension compared to the baseline of 0.38 microvolts (Baseline P50-N95: mean 0.92 microvolts, a standard deviation: 0.29 microvolts; P50-N95 at 60 days: mean 1.30 microvolts, a standard deviation: 0.25 microvolts).

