9.2 General methodology

Data from repetitions of visual acuity tests, PERG, VEP, OCT will be expressed as the average difference between two recordings obtained during separate sessions + / - the standard deviation of this difference. The 95% confidence limits of the test-retest variability will be established by assuming a normal distribution of the data, after verification using the Anderson-Darling and Kolmogorov-Smirnov tests, calculating the average of the differences and the relative standard deviations.

For each group (NAION Control eyes and NAION eyes Treated with Cisticoline), differences in visual acuity values, PERG and VEP and OCT responses measured at 6 and 9 months from

baseline will be assessed using ANOVA and the $p < 0.05$ value will be considered significant. Multiple comparisons will be made using the Tukey and Games-Howell methods, establishing the value of the error rates at 5%.

Correlations between the electric-physiological measurements (PERG/VEP) and field of view measurements, normalized in logarithmic value, both at Baseline and at each follow-up time, for each group will be performed using Pearson's test and the $p < 0.05$ value will be considered significant.

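### Section 5.1 balances the arms on age, refraction, field defect and acuity, section 6 describes assignment without them, and 9.2 gives no between-group model that uses them or the outcome's baseline

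*Combined protocol and SAP*

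**What the plan says.** **Allocation, section 5.1 (Trial Plan).** "Randomization will be done by dividing patients with similar characteristics including age, refraction and visual impairment (perimeter defect and visual acuity) into two groups". No strata, blocks, pairing or minimisation rule is given.

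**Allocation, section 6 (Assignment and Masking).** Patients are assigned "in sequential order of presentation of the patient (with a 1:1 probability of being assigned to one or the other group"), with the aim of equal numbers. None of the four factors from 5.1 appears.

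**Analysis, section 9.2 (General methodology).** "For each group (NAION Control eyes and NAION eyes Treated with Cisticoline), differences in visual acuity values", and likewise PERG, VEP and OCT measures, at 6 and 9 months from "baseline will be assessed using ANOVA and the $p < 0.05$ value will be considered significant". Tukey and Games-Howell comparisons follow. No treatment term, covariate or treated-versus-control test is named.

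**Intended comparison.** Section 2.2 (objective 3) and section 10.1 both promise a comparison with untreated patients, and 5.1 says that the two groups are there to identify a specific effect of citicoline. A between-group contrast will therefore have to be made, although 9.2 does not define it.

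**Unit.** Section 5.1 counts eyes and expects both eyes of a bilateral patient to enter. Section 4 allows as few as 16 patients for 32 eyes.

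**The concern.** An analysis should reflect the restrictions used in assignment. Balancing the arms on a prognostic factor removes that factor's contribution to the chance difference between arms. A model that leaves the factor out still counts its spread as random error. The reported standard error is then larger than the real one, intervals are too wide and the test is conservative.

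Without balancing, the unadjusted test is valid but still gives away precision that a baseline measurement would supply. Visual acuity, field, PERG, VEP and OCT are all due at T0 under section 5.4, so each outcome's baseline will be on file. With at most 32 eyes, that precision is worth having. An unspecified between-group model also leaves the choice of covariates open until the data are seen.

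**Working it through.** **1. The plan's own sample size.** Section 9.1 gives acuity as "baseline visual acuity: mean 0.621 LogMAR, a standard deviation: 0.122 LogMAR; visual acuity at 60 days: mean 0.271 LogMAR, a standard deviation: 0.107 LogMAR" and PERG as "Baseline P50-N95: mean 0.92 microvolts, a standard deviation: 0.29 microvolts; P50-N95 at 60 days: mean 1.30 microvolts, a standard deviation: 0.25 microvolts". It uses 90% power, 5% alpha and two independent samples. I used a two-sided two-sample t test with SD = √((s₁² + s₂²)/2).
- Acuity: SD = √((0.122² + 0.107²)/2) = 0.1147; d = 0.35/0.1147 = 3.05. Four eyes per group give 94.6% power; the stated 5 give 98.7%.
- PERG: SD = √((0.29² + 0.25²)/2) = 0.2707; d = 0.38/0.2707 = 1.40. Twelve per group give 90.7%, as stated.
- VEP: the text has no baseline SD value. Assuming 9.8 ms at both times, 11 per group give 92.7%, as stated.
- Inflation: 12 × 1.3 = 15.6, rounded to 16.

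The figures reproduce, and none assumes covariate adjustment.

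**2. Between-group test of change if the arms are closely matched on baseline.** Assumptions: 16 v 16, one eye per patient, outcome SD of 1, baseline-to-follow-up correlation r (not in the documents; range 0.4 to 0.8).
- SE that the unadjusted test reports: √(2(1 − r) × 2/16).
- Real SE under matching: √((1 − r²) × 2/16).
- Ratio: √(2/(1 + r)).
- Type I error: two-sided tail of t on 30 df beyond 2.042 × ratio.

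| r | Reported SE | Real SE | Ratio | Type I error |
|---|---|---|---|---|
| 0.4 | 0.387 | 0.324 | 1.195 | 2.1% |
| 0.6 | 0.316 | 0.283 | 1.118 | 3.0% |
| 0.8 | 0.224 | 0.212 | 1.054 | 4.0% |

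Simulation agrees (about 2.0%, 3.1% and 3.8%), and adjusting for baseline restores about 5%. Looser matching moves the unadjusted test towards 5%.

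**3. The same test under simple 1:1 allocation, as in section 6.** The unadjusted SE is correct and type I error is about 5%. Adjustment then only adds precision.

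**4. Power.** Simulated at assumed effects of 1.0, 0.9 and 0.65 SD for r = 0.4, 0.6 and 0.8:

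| Allocation | Unadjusted change | Baseline-adjusted |
|---|---|---|
| Matched | 71 / 80 / 81% | 83 / 87 / 84% |
| Simple 1:1 | 70 / 78 / 79% | 83 / 86 / 83% |

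Adding three covariates that prove non-prognostic cuts the matched figures to 79 / 82 / 79%. At r = 0.8 that is no better than no adjustment.

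**5. On the plan's own scale.** At 16 per group the acuity SE is 0.1147 × √(2/16) = 0.0406. If covariates explain a share R² of the variance (assumed 0.10, 0.25 or 0.50), multiplying by √(1 − R²) gives 0.0385, 0.0351 or 0.0287. Unadjusted power at the planned effects is above 99.9% for acuity and about 97% for PERG. For an assumed acuity effect of 0.10 LogMAR it is 67%, against 71%, 79% or 92% with adjustment.

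**6. The ANOVA as written.** If it is a repeated-measures analysis within a group, a factor fixed within the eye cannot change the SE. A worked example gives 0.0206 with and without such a factor. If visits are treated as independent, the SE in that example is 0.0440. Adding the factor lowers it to 0.0305, but pairing by eye lowers it to 0.0206, so pairing is the full remedy.

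**7. Two eyes per patient.** If every patient is bilateral, the true SE of a mean is √(1 + ρ) times the naive one. For an assumed inter-eye correlation ρ of 0.3 to 0.7 that is 1.14 to 1.30. With matching on patient mean acuity and all 16 patients bilateral, the simulated type I error of the unadjusted test was 4% to 12%, above 5% in 8 of 9 settings.

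**The case against.** A reader might infer that the plan's error bars are too wide and that the trial loses power as designed. The documents do not support that, for four reasons.

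- **No such standard error is in the plan.** The 9.2 ANOVA is within each arm, so it yields no treated-versus-control SE that could be too wide. This stands. The missing between-group test is the larger gap, and the conservatism is conditional on how that test is eventually done.
- **Balanced allocation is not established.** Section 6 names no factor, and 5.1 gives no mechanism. This stands. The type I error result depends on 5.1 being followed; the precision gain does not.
- **Bilateral eyes act in the opposite direction.** This stands, and the mix of unilateral and bilateral patients is unknown. It is a separate fault and does not offset the first in any controlled way.
- **Power is ample at the planned effects.** This is true of the figures in 9.1. They are, however, differences from baseline after 60 days of an oral suspension, given at 1600 mg/day according to section 1.2. They are not treated-versus-control differences at 6 or 9 months with the present product and dose. High power at those values says little about a smaller between-group effect.

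It may also be said that a difference from baseline already uses the baseline value. It does so only with the slope fixed at 1. The unadjusted comparator in the power table is exactly that change score, and it is still less precise when r is below 1.

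**Conclusion.** The point holds conditionally. Sections 5.1 and 6 do not describe the same allocation, and 9.2 specifies neither a between-group model nor any use of the baseline value or balancing factors in one.

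If assignment is balanced as in 5.1, an unadjusted comparison of change is conservative to the extent shown in step 2. If it is simple 1:1, the error rate is correct, and the loss at the assumed effects is about 4 to 13 percentage points of power (79% against 83% at r = 0.8; 70% against 83% at r = 0.4). These figures rest on assumed correlations and effects and on one eye per patient.

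No net direction of error can be claimed for the trial as planned, and no material power loss at the effects in 9.1. Nor is adjustment for all four factors a free gain with so few eyes. The baseline of the outcome is the term that earns its place.

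**What to change.** - **Allocation.** Reconcile 5.1 and 6 into one procedure. If factors are used, name them and state the mechanism; if not, remove the claim of balance from 5.1.
- **Analysis.** In 9.2, specify for each outcome a treated-versus-control model with treatment and the baseline value of that outcome. Add only the factors actually used in assignment, and keep them few. Report the treatment difference with its 95% confidence interval.
- **Two eyes.** Allow for eyes of the same patient, for example with a patient random effect or patient-clustered standard errors. Use a small-sample correction, since there may be as few as 16 patients.

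**Cost.** The change takes a short paragraph in 9.2 and one in 5.1 or 6, with no added patients or visits. Treatment and one baseline term leave 32 − 3 = 29 residual degrees of freedom at the level of eyes, and each further factor takes at least one more. If added factors are not prognostic, part or all of the gain is lost. Allowing for paired eyes will widen intervals where many patients are bilateral, which is the honest result.

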5.2 Schematic diagram of the trial plan

The schematic diagram of the study is shown below.

	Baseline		
Visit	T0	T1	T2
Months		6	9
Time window		± 10 days	± 10 days
Informed consent	✓		
Demographic data	✓		
Medical records	✓		
Visual Field	✓	✓	✓
PERG	✓	✓	✓
PEV	✓	✓	✓
OCT	✓	✓	✓
Concomitant diseases	✓	✓	✓
Previous treatments	✓		
Concomitant treatments	✓	✓	✓
Complete ophthalmological examination: visual acuity anterior and posterior biomicroscopy ophthalmoscopy intraocular pressure			
Inclusion/exclusion criteria	✓		✓
Randomization	✓		
Compliance	✓	✓	✓
Delivery of food supplement	✓		
Incidents	✓	✓	✓

5.3 Trial term and visits

The study will have a total duration of 9 months, during which period the patients will have 3 visits:

- baseline visit T0
- visit at 6 months T1
- visit at 9 months T2

5.4 Scheduled visits

The visits will be made at baseline, at 6 and 9 months of follow-up, not knowing to which group the patient belongs. The key will be opened only at the end of the second treatment period in order to assess the initial effects (after 9 months).

After screening, the patients enrolled will make a baseline visit during which they will be randomized into one of two groups. The visits will take place 6 and 9 months after the baseline visit.

At the baseline and each visit a complete ophthalmic examination will be performed, including the following assessments: corrected visual acuity, biomicroscopy, indirect ophthalmoscopy, measurement of intraocular pressure with Goldmann applanation tonometer, field of vision testing, recording of PERG and VEP, imaging of the optic nerve and retinal nerve fibre layer with OCT.

5.5 Outcomes

The visual function will be determined by [Visual] acuity assessment, the function of retinal ganglion cells RGC will be assessed by electroretinogram (PERG) and the optic nerve function will be evaluated using the Visual Evoked Potential (VEP).

The primary objective is to evaluate the stabilisation and/or improvement in visual acuity.

Secondary objectives include stabilising and/or improving RGC functionality and optic nerve function assessed with the recording of PERG and VEP. Correlations will also be evaluated between stabilisation and/or function improvement of RGC and the optic nerve with changes in the visual field and the morphology of the optic nerve head (evaluated by OCT).

5.5.1. Psychophysical Evaluations

a) Visual Acuity (VA)

The visual acuity (VA) examination for distance will be made with optotype projection of letters at 4 meters and the use of trial lenses in mesopic environment. Backlit ETDRS (Early Treatment Diabetic Retinopathy Study) Cards will be used for measuring the best visual acuity for distance. The expressed value acquired, LogMAR (logarithm of the minimum angle of resolution), will be converted to a decimal Snellen fraction according to the equivalence tables.

The visual acuity examination for near vision will be performed in the presence of good lighting with trial lenses added to the lens in use by the patient or to the lens measured for distance (best optical correction). The examination is performed with the aid of optical tables for near vision and measured according to the maximum quantity of vision in terms of character for near vision (I character for near vision indicates maximum acuity, X character indicates worst acuity for near vision).

b) Visual Field (VF)

A static perimetry will be performed for the visual field (VF) measurements (Humphrey 30-2 SITA Standard program, with losses of fixation, rate of false positives and false negatives that must be <20%). The main indexes of the Humphrey perimetry are: Mean Deviation (MD) and Pattern Standard Deviation (PSD). The MD establishes the average of the defect obtained at all the points tested, considering the increasing dispersion of sensitivity values compared to the data obtained in normal persons based on the eccentricity and thus able to represent a severity index of the global damage. PSD indicates the homogeneity of the distribution of the visual field defect and therefore provides information on local damage.

5.5.2. Electrophysiological Evaluations

a) Pattern electroretinogram (PERG)

The PERG shows the bioelectric activity of the innermost layers of the retina (ganglion cells, their fibres). PERG response is characterised by a series of waves with three successive peaks, with polarity negative, positive and negative respectively. In normal people, these peaks have the following implicit times: 35, 50 and 95 msec (N35, P50 and N95). An increase in the N35, P50 and N95 times and a decrease in amplitude N35-P50 and P50-N95 was found in glaucoma patients. These abnormalities in PERG are significantly related to visual field defects and to a reduction in the thickness of the layer of nerve fibres.

Also, PERG has shown a high clinical capacity (sensitivity: 100%, specificity: 100%) to detect malfunctions of the ganglion cells in glaucoma patients (Parisi et al. 2006).

b) Visual evoked potentials (VEP)

VEPs reflect the bioelectric activity of the visual cortex in response to visual stimulation and thus evaluate the function of the visual pathway as a whole. VEP response is characterised by a series of waves with three successive peaks, with polarity negative, positive and negative respectively. In normal people, these peaks have the following times: 75, 100 and 145 msec (N75, P100 and N145). An increase in the N75, P100 and N145 times and a decrease in amplitude N75-P100 and P100-N145 was found in glaucoma patients. These VEP abnormalities are significantly correlated with visual field defects. Also, VEP has shown a high clinical capacity (sensitivity: 100%, specificity: 100%) to detect a delay in the neural conduction along the visual pathways in patients with glaucoma (Parisi et al. 2006). Comparing VEP and PERG times allows for the obtaining a neural conduction index in the postretinal visual pathways. In fact, the difference between the VEP P100 and P50 times is known as "Retino-cortical Time (RCT)".

5.5.3. Morphological Evaluation

Optical coherence tomography (OCT))

OCT is a non invasive imaging technique that allows for the obtaining of high-resolution images in section of the retina and its individual layers and the optic nerve, using light radiation as an energy source. Recently a new generation of OCT has been developed and introduced on the market, a high-definition Spectral Domain OCT (HD-OCT), which in comparison to the previous version allows a faster capture rate of the image and a higher spatial resolution.

5.6 Efficiency parameters

- For the VA examination, the visual acuity values will be recorded for distance and near vision corrected with the best optical correction.
- For the visual field examination, the following parameters will be recorded: mean deviation (MD), pattern standard deviation (PSD), number of points, with $p < 5\%$ and $< 1\%$ in the pattern deviation map and the total deviation map.
- Each PERG examination will record the following parameters: latency P50 and amplitude P50-N95.

- The following parameters will be recorded for each VEP test: latency N75 and P100, amplitude N75-P100 and P100-N145
- For each OCT imaging session the following parameters will be recorded: the average thickness of the retinal nerve fibre layer and the thickness divided according to sectors.
- At baseline and at each control visit (6 and 9 months) a complete eye examination will be performed including the following assessments: corrected visual acuity, biomicroscopy, indirect ophthalmoscopy, measurement of intraocular pressure with Goldmann applanation tonometer, field of vision testing, recording of PERG and VEP, imaging of the optic nerve and retinal nerve fibre layer with OCT.

